14.4.4. Other Assessments

- Vital signs include systolic and diastolic blood pressure, pulse, and body temperature, and should be measured pre-dose. The subject must rest quietly for 5 minutes prior to blood pressure and pulse measurements. Weight will be collected at Baseline/Entry Visit and at the time of first autoinjector use at selected sites.
- The MSIS-29 must be administered prior to the subject's visit with the *Study Neurologist*.
- Subject assessment of injection pain using a VAS should be completed as soon as possible after the injection is administered but no later than 10 to 30 minutes post-injection.
- The first 4 DAC HYP injections (i.e., Weeks 0 through 12) must be given in the clinic. The first of these injections must be given by study personnel. At subsequent visits, subjects and/or caregivers will be instructed on DAC HYP self-administration and may administer their scheduled dose under staff supervision. After the subject completes the required in-clinic injections (i.e., after Week 12), DAC HYP may be dispensed to subjects for at-home administration if the subject chooses. If necessary, drug dispensation may occur at monthly intervals.
- Additional visits to assess elevated LFTs, cutaneous events, or PK/■ markers may be required as described in Section 11.7.

CONFIDENTIAL

The information contained herein may not be used, disclosed, or published without the written consent of Biogen MA Inc.

14.5. Definition of MS Relapse and Disability Progression

14.5.1. MS Relapse

Relapses are defined as new or recurrent neurological symptoms not associated with fever or infection, lasting at least 24 hours, and accompanied by new objective neurological findings upon examination by the *Study Neurologist** or their backup. The subject must have objective signs on the examination confirming the event.

*When possible subjects should be evaluated by the same neurologist assigned to them in the parent study.

New or recurrent neurologic symptoms that evolve gradually over months should be considered disability progression, not an acute relapse. New or recurrent neurological symptoms that occur less than 30 days following the onset of a protocol-defined relapse should be considered part of the same relapse. Management of MS relapse is described in Section 14.6.

14.5.2. Disability Progression

Disability progression can only be confirmed from the EDSS scores obtained according to the protocol-defined schedule of assessments at regular visits, and is defined as one of the following:

- at least a 1.0-point increase on the EDSS from a baseline EDSS ≥ 1.0 that is sustained for 24 weeks, or
- at least a 1.5-point increase on the EDSS from a baseline EDSS < 1.0 that is sustained for 24 weeks

14.6. Management of MS Relapse

Subjects who experience new or worsening neurological symptoms must contact the *Nurse* or *Study Neurologist* or their backup within 48 hours after the onset of symptoms. A standardized Suspected Relapse Questionnaire will be completed to determine the necessity of an Unscheduled Relapse Assessment Visit.

If required, the subject will then be evaluated in person by the *Study Neurologist* not more than 72 hours after the onset of the symptoms. At the Unscheduled Relapse Assessment Visit, the *Study Neurologist* is to perform a relapse assessment and obtain an EDSS score. New objective findings on neurological examination performed by the *Study Neurologist** are required to determine if a suspected protocol-defined relapse has occurred. Treatment of an acute relapse event with intravenous methylprednisolone (IVMP) [or equivalent] may proceed at the discretion of the *Study Neurologist* after the examination and will not affect the subject's eligibility to continue in the study.

*When possible subjects should be evaluated by the same neurologist assigned to them in the parent study.

Subjects who prematurely discontinue study treatment should complete safety follow-up evaluations (see Section 4.2 and Section 13).

CONFIDENTIAL

The information contained herein may not be used, disclosed, or published without the written consent of Biogen MA Inc.

Subjects who permanently discontinue DAC HYP treatment should complete the visit schedule described in Section 11.8.

14.7. Cutaneous Events

Subjects who experience a mild or moderate cutaneous AE that is associated with more than 1 systemic symptom or sign, a severe cutaneous AE (with or without systemic symptoms or signs), or a serious cutaneous AE (with or without systemic symptoms or signs) must be referred to and evaluated and managed by the *Study Dermatologist* as per Section 11.7.3. An Unscheduled Dermatology Assessment Visit will be performed, at which time a photograph will be taken, whenever a subject experiences a mild or moderate cutaneous AE that is associated with more than 1 systemic symptom or sign, a severe cutaneous AE (with or without systemic symptoms or signs), or a serious cutaneous AE (with or without systemic symptoms or signs), per Table 6. Subjects who develop a mild or moderate cutaneous AE that is not associated with more than 1 systemic symptom or sign do not need to be evaluated by the *Study Dermatologist*; the *Study Neurologist* can complete the Unscheduled Dermatology Assessment Visit as soon as possible.

If a generalized allergic or hypersensitivity reaction to study treatment is confirmed, study treatment must be permanently discontinued as per Section 11.8.

14.8. Unscheduled Hepatic Assessment Visit

The following tests/assessments will be performed as soon as possible (but within 1 week) after discontinuation of study treatment for subjects who are required to discontinue dosing due to elevated LFTs as described in Table 6 and Section 11.8.

- Physical examination and vital signs
- Comprehensive hepatic panel
- Recording of concomitant therapy
- Monitor and record AE/SAEs
- Protocol compliance and DAC HYP accountability
- LFTs (ALT/SGPT, AST/SGOT, alkaline phosphatase, total bilirubin, and GGT only)

14.9. Lymphadenopathy and Lymphadenitis Events

Subjects who experience a clinically significant event of lymphadenopathy or lymphadenitis should be referred to a specialist as per Section 11.7.5.

Interruption or discontinuation of DAC HYP treatment due to events of lymphadenopathy or lymphadenitis is a clinical decision that should take the overall benefit-risk assessment of therapy into consideration. Subjects who discontinued study treatment for any reason while presenting with ongoing lymphadenopathy or lymphadenitis should be followed until the lymphadenopathy or lymphadenitis has stabilized or resolved or the study has terminated, whichever comes first.

CONFIDENTIAL

The information contained herein may not be used, disclosed, or published without the written consent of Biogen MA Inc.

14.10. Post-Treatment Safety Follow-Up Visit Schedule for All Subjects

All subjects should complete the following schedule of safety follow-up visits after their last dose of DAC HYP:

- End of Treatment Visit (i.e., the assessments required at Week 240). For subjects who prematurely discontinue study treatment before Week 240, these assessments should be performed 4 weeks (± 4 days) after the subject's last dose of DAC HYP.
- Post-treatment safety follow-up visits at 8, 12, 16, 20, and 24 weeks after the subject's last dose. The details of these visits are shown in [Table 5](#).

Note: Subjects who complete Week 144 of DAC HYP treatment in Study 205MS303 and are in the safety follow-up period per the original protocol, will have the option to restart DAC HYP treatment from Week 156 Visit in Study 205MS303 (see [Table 4](#)) as long as they meet the eligibility criteria (Section [8](#)).

CONFIDENTIAL

The information contained herein may not be used, disclosed, or published without the written consent of Biogen MA Inc.

15. SAFETY DEFINITIONS, MONITORING, AND REPORTING

Throughout the course of the study, every effort must be made to remain alert to possible AEs. If an AE occurs, the first concern should be for the safety of the subject. If necessary, appropriate medical intervention should be provided.

At the signing of the ICF, each subject must be given the names and telephone numbers of study site staff for reporting AEs and medical emergencies.

15.1. Definitions

15.1.1. Serious Pretreatment Event

A serious pretreatment event is any event that meets the criteria for SAE reporting (as defined in Section 15.1.3) and occurs after the subject signs the ICF, but before administration of study treatment.

15.1.2. Adverse Event

An AE is any untoward medical occurrence in a patient or clinical investigation subject administered a pharmaceutical product and that does not necessarily have a causal relationship with this treatment. An AE can therefore be any unfavorable and unintended sign (including an abnormal laboratory finding), symptom, or disease temporally associated with the use of a medicinal (investigational) product, whether or not related to the medicinal (investigational) product.

15.1.3. Serious Adverse Event

An SAE is any untoward medical occurrence that at any dose:

- results in death
- in the view of the Investigator, places the subject at immediate risk of death (a life-threatening event); however, this does not include an event that, had it occurred in a more severe form, might have caused death
- requires inpatient hospitalization or prolongation of existing hospitalization
- results in persistent or significant disability/incapacity, or
- results in a congenital anomaly/birth defect.

An SAE may also be any other medically important event that, in the opinion of the Investigator, may jeopardize the subject or may require intervention to prevent one of the other outcomes listed in the definition above. Examples of such medical events include allergic bronchospasm requiring intensive treatment in an emergency room or convulsions occurring at home that do not require an inpatient hospitalization.

CONFIDENTIAL

The information contained herein may not be used, disclosed, or published without the written consent of Biogen MA Inc.

15.2. Monitoring and Recording Events

15.2.1. Serious Pretreatment Events

A serious pretreatment event experienced by the subject after signing and dating the ICF but before administration of study treatment is to be recorded on the SAE Form and faxed to the contract research organization (CRO) within 24 hours of the study site staff becoming aware of the event (see Section 15.2.5).

15.2.2. Adverse Events

Any AE experienced by the subject between the time of signing the ICF and subject's final visit is to be recorded on the CRF, regardless of the severity of the event or its relationship to study treatment.

15.2.3. Serious Adverse Events

Any SAE experienced by the subject between the time of the first dose of study treatment and subject's final visit is to be recorded on an SAE Form, regardless of the severity of the event or its relationship to study treatment. SAEs must be reported to the CRO.

Any SAE ongoing when the subject completes the study or discontinues from the study will be followed by the Investigator until the event has resolved, stabilized, or returned to baseline status.

Subjects will be followed for all SAEs until the subject's final visit. Thereafter, the event should only be recorded if the Investigator considers it related to study treatment.

15.2.4. All Events

All events must be assessed to determine the following:

- If the event meets the criteria for an SAE as defined in Section 15.1.3.
- The relationship of the event to study treatment as defined in Section 15.3.1.
- The severity of the event as defined in Section 15.3.2.

15.2.5. Immediate Reporting of Serious Adverse Events

In order to adhere to all applicable laws and regulations for reporting an SAE, the study site must formally notify the CRO within 24 hours of the study site staff becoming aware of the SAE. It is the Investigator's responsibility to ensure that the SAE reporting information and procedures are used and followed appropriately.

CONFIDENTIAL

The information contained herein may not be used, disclosed, or published without the written consent of Biogen MA Inc.

Reporting Information for SAEs

Any Serious Event that occurs between the time the subject has signed informed consent and subject's final visit must be reported to the CRO within 24 hours of the study site staff becoming aware of the event. **Thereafter, the event should only be recorded if the Investigator considers it related to study treatment.**

A report pertaining to an event that occurs between the time the subject has signed informed consent and subject's final visit **must be submitted** to the CRO regardless of the following:

- whether or not the subject has undergone study-related procedures
- whether or not subject has received study treatment
- the severity of the event
- the relationship of the event to study treatment

To report initial or follow-up information on a Serious Event, fax a completed SAE form to the following:

North America: [REDACTED]
Latin America: [REDACTED]
Europe and Asia Pacific: [REDACTED]

(Country-specific fax numbers are provided in the Study Reference Guide.)

15.2.5.1. Deaths

Death is an outcome of an event. The event that resulted in death should be recorded and reported on the appropriate CRF. All causes of death must be reported as SAEs. The Investigator should make every effort to obtain and send death certificates and autopsy reports to Biogen SABR or designee.

15.3. Safety Classifications

15.3.1. Relationship of Events to Study Treatment

The following definitions should be considered when evaluating the relationship of AEs and SAEs to the study treatment:

CONFIDENTIAL

The information contained herein may not be used, disclosed, or published without the written consent of Biogen MA Inc.

Relationship of Event to Study Treatment	
Not related	An adverse event will be considered “not related” to the use of the investigational drug if there is not a possibility that the event has been caused by the product under investigation. Factors pointing toward this assessment include, but are not limited to: the lack of reasonable temporal relationship between administration of the drug and the event, the presence of a biologically implausible relationship between the product and the adverse event (e.g., the event occurred before administration of drug), or the presence of a more likely alternative explanation for the adverse event.
Related	An adverse event will be considered “related” to the use of the investigational drug if there is a possibility that the event may have been caused by the product under investigation. Factors that point toward this assessment include, but are not limited to: a positive rechallenge, a reasonable temporal sequence between administration of the drug and the event, a known response pattern of the suspected drug, improvement following discontinuation or dose reduction, a biologically plausible relationship between the drug and the adverse event, or a lack of an alternative explanation for the adverse event.

15.3.2. Severity of Events

The following definitions should be considered when evaluating the severity of AEs and SAEs:

Severity of Event	
Mild	Symptom(s) barely noticeable to subject or does not make subject uncomfortable; does not influence performance or functioning; prescription drug not ordinarily needed for relief of symptom(s) but may be given because of personality of subject.
Moderate	Symptom(s) of a sufficient severity to make subject uncomfortable; performance of daily activity is influenced; subject is able to continue in study; treatment for symptom(s) may be needed.
Severe	Symptom(s) cause severe discomfort; symptoms cause incapacitation or significant impact on subject’s daily life; severity may cause cessation of treatment with study treatment; treatment for symptom(s) may be given and/or subject hospitalized.

15.3.3. Expectedness of Events

Expectedness of all AEs will be determined according to the Investigator’s Brochure.

15.4. Prescheduled or Elective Procedures or Routinely Scheduled Treatments

A prescheduled or elective procedure or a routinely scheduled treatment will not be considered an SAE, even if the subject is hospitalized; the study site must document all of the following:

- The prescheduled or elective procedure or routinely scheduled treatment was scheduled (or was on a waiting list to be scheduled) prior to obtaining the subject’s consent to participate in the study.
- The condition requiring the prescheduled or elective procedure or routinely scheduled treatment was present before and did not worsen or progress in the opinion of the

CONFIDENTIAL

The information contained herein may not be used, disclosed, or published without the written consent of Biogen MA Inc.

Investigator between the subject's consent to participate in the study and the time of the procedure or treatment.

- The prescheduled or elective procedure or routinely scheduled treatment is the sole reason for the intervention or hospital admission.

15.5. Procedures for Handling Special Situations

15.5.1. Overdose

An overdose is any dose of study treatment given to a subject or taken by a subject that exceeds the dose described in the protocol. Overdoses are not considered AEs; however, all overdoses should be recorded on an Overdose Form and faxed to the CRO within 24 hours. An overdose should be reported even if it does not result in an AE. Overdoses do not need to be recorded in the CRF; dosing information is recorded on a CRF.

15.5.2. Medical Emergency

In a medical emergency requiring immediate attention, study site staff will apply appropriate medical intervention, according to current standards of care. The Investigator or designee should contact the CRO Medical Monitor at one of the following phone numbers:

North America (USA and Canada): [REDACTED]

Latin America: [REDACTED]

Europe and Asia Pacific: [REDACTED]

15.5.3. Contraception Requirements

All women of childbearing potential must practice effective contraception during the study and be willing and able to continue contraception for 4 months after their last dose of study treatment.

For the purposes of this study, women of childbearing potential are defined as all women physiologically capable of becoming pregnant, UNLESS they meet one of the following conditions:

- Postmenopausal: 12 months of natural (spontaneous) amenorrhea or 6 weeks after surgical bilateral oophorectomy with or without hysterectomy
- Posthysterectomy

For the purposes of the study, effective contraception is defined as follows:

For females:

- Using 1 or more of the following acceptable methods of contraception: surgical sterilization (e.g., bilateral tubal ligation), intrauterine contraception/device, hormonal contraception, or any 2 barrier methods (a combination of male or female condom with spermicide; diaphragm, sponge, cervical cap)

CONFIDENTIAL

The information contained herein may not be used, disclosed, or published without the written consent of Biogen MA Inc.

- True abstinence, when this is consistent with the preferred and usual lifestyle of the subject, can be considered an acceptable method of contraception based on the evaluation of the Investigator who should also take into consideration the duration of the clinical trial. Periodic abstinence (e.g., calendar, ovulation, symptothermal, post-ovulation methods) and withdrawal are not considered acceptable methods of contraception.

15.5.4. Pregnancy

Subjects should not become pregnant during the study. If a female subject becomes pregnant, study treatment must be discontinued *immediately*.

The Investigator must report the pregnancy by faxing the appropriate form to Pharmacovigilance at the CRO within 24 hours of the study site staff becoming aware of the pregnancy (refer to Section 15.2.5 for reporting information). The Investigator or study site staff must report the outcome of the pregnancy to Pharmacovigilance at the CRO.

Please note that congenital abnormalities/birth defects in the offspring of male or female subjects should be reported when conception occurred during the study treatment period.

15.5.5. Regulatory Reporting

Suspected Unexpected Serious Adverse Reactions (SUSARs) are SAEs that are unexpected and judged by the Investigator or the Sponsor to be related to the study treatment administered.

Biogen Safety and Benefit-Risk Management (SABR) will report SUSARs to the appropriate regulatory authorities and Investigators as required, according to local law.

15.6. Investigator Responsibilities

The Investigator's responsibilities include the following:

- Monitor and record all AEs, including SAEs, regardless of the severity or relationship to study treatment.
- Determine the seriousness, relationship, and severity of each event.
- Determine the onset and resolution dates of each event.
- Monitor and record all pregnancies and follow-up on the outcome of the pregnancy.
- Complete an SAE form for each serious event and fax it to the CRO within 24 hours of the study site staff becoming aware of the event.
- Pursue SAE follow-up information actively and persistently. Follow-up information must be reported to the CRO within 24 hours of the study site staff becoming aware of new information.
- Complete an Adverse Event of Special Interest form for each transaminase elevation, hepatic event, and cutaneous event as described in the protocol and fax it to the CRO as soon as possible following the study site staff becoming aware of the event.
- Ensure all AE and SAE reports are supported by documentation in the subjects' medical records.

CONFIDENTIAL

The information contained herein may not be used, disclosed, or published without the written consent of Biogen MA Inc.

- Report SAEs to local ethics committees, as required by local law.

15.7. Biogen Responsibilities

Biogen's responsibilities include the following:

- Before study site activation and subject enrollment, the Clinical Monitor or designee is responsible for reviewing with study site staff the definitions of AE and SAE, as well as the instructions for monitoring, recording, and reporting AEs and SAEs.
- Biogen is to notify all appropriate regulatory authorities, central ethics committees, and Investigators of SAEs, as required by local law, within required time frames.

CONFIDENTIAL

The information contained herein may not be used, disclosed, or published without the written consent of Biogen MA Inc.

16. STATISTICAL METHODS AND DETERMINATION OF SAMPLE SIZE

16.1. Description of Objectives

See Section 6.1, Objectives.

16.2. Description of Endpoints

See Section 6.2, Endpoints.

16.3. Demography and Baseline Disease Characteristics

Demographic data collected at baseline will be summarized (i.e., age, gender, ethnicity, and weight). Medical history and baseline characteristic data (e.g., EDSS, number of relapses in the previous study, MRI endpoints) will also be summarized.

16.4. Safety and Efficacy

16.4.1. Analysis Population

Study 205MS303 Safety Population

The safety population will include all subjects who received at least 1 dose of DAC HYP in Study 205MS303. All safety analyses will be completed on the safety population.

Study 205MS303 Intent-to-Treat Population

The intent-to-treat (ITT) population will include all subjects who received at least 1 dose of DAC HYP in Study 205MS303. This population will be utilized for the efficacy analyses.

Study 205MS301 and Study 205MS303 Intent-to-Treat population

This population will include all subjects randomized to DAC HYP or Avonex in Study 205MS301 and received at least one dose of DAC HYP in Study 205MS303.

16.4.2. General Methods of Analysis

Summary statistics will be presented. For continuous endpoints, summary statistics will generally include the number of subjects with data, mean, standard deviation, median, and range. Categorical endpoints will include the number of subjects with data and the percentage in each category.

Analyses will generally be descriptive in nature and will focus on data collected during Study 205MS303 only. However, for relevant efficacy analyses, the data may be summarized by previous treatment group (Avonex or DAC HYP). Also, statistical comparisons may be made between efficacy in Study 205MS301 and efficacy in Study 205MS303 among subjects previously randomized to Avonex in Study 205MS301.

All statistical tests will be 2-sided with an overall Type I error of 5%. Adjustments for multiple comparisons will not be considered.

CONFIDENTIAL

The information contained herein may not be used, disclosed, or published without the written consent of Biogen MA Inc.

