6.1.3. Exploratory Objective

6.2. Endpoints

6.2.1. Primary Endpoints

- Incidence of AEs and SAEs

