6.2.2. Secondary Endpoints

- Relapse outcomes: annualized relapse rate (ARR) and proportion of subjects who relapse
- Sustained disability progression defined by at least a 1.0-point increase on the Expanded Disability Status Scale (EDSS) score from a baseline EDSS ≥ 1.0 that is sustained for 24 weeks, or at least a 1.5-point increase on the EDSS from a baseline EDSS < 1.0 that is sustained for 24 weeks
- Magnetic Resonance Imaging (MRI) outcomes: total number and volume of new or newly enlarging T2 hyperintense lesions, Gd-enhancing lesions, T1 hypointense lesions, and brain volume change on brain MRI
- Change in Multiple Sclerosis Functional Composite (MSFC) score

CONFIDENTIAL

The information contained herein may not be used, disclosed, or published without the written consent of Biogen MA Inc.

- Change in EDSS score
- Change in Symbol Digit Modalities Test (SDMT) score
- Change in 3-Second Paced Auditory Serial Addition Test (PASAT 3) score
- Proportion of subjects who are free from disease activity.
- Change in Multiple Sclerosis Impact Scale-29 (MSIS-29) physical and psychological scores
- Change in quality of life as assessed by the European Quality of Life, 5 dimensions (EQ-5D and EQ-VAS)
- Change in direct health resource utilization (HRU; hospitalizations, emergency room visits, and unscheduled neurologist visits)
- Change in treatment satisfaction as assessed by the subject
- Change in subject productivity as assessed by the Health Related Productivity Questionnaire (HRPQ)
- Changes in clinical laboratory assessments (hematology and blood chemistry)
- Local tolerability as assessed by subject-reported injection site pain (VAS) and clinician injection site assessments
- Incidence of anti-drug antibodies (ADAs) to DAC HYP over time
- Incidence of neutralizing antibodies (NAbs) to DAC HYP over time

CONFIDENTIAL

The information contained herein may not be used, disclosed, or published without the written consent of Biogen MA Inc.

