16.4.5. Efficacy Endpoints Analyses

Annualized Relapse Rate

Relapses will be summarized over the follow-up period in Study 205MS303. For subjects in Study 205MS301 and Study 205MS303 ITT population, relapses may be summarized over the combined study period (Studies 205MS301 and 205MS303).

A negative binomial regression model will be used to estimate the adjusted ARR.

Proportion of Subjects with a Relapse

The proportion of subjects relapsed will be estimated using a Kaplan-Meier curve.

Disability Progression

Sustained disability progression is defined as at least a 1.0 point increase on the EDSS from baseline EDSS ≥ 1.0 that is sustained for 24 weeks, or at least a 1.5 point increase on the EDSS from baseline EDSS < 1.0 that is sustained for 24 weeks. The proportion of subjects with progression will be summarized using a Kaplan-Meier curve. In addition, summary statistics for EDSS and for the change from baseline in EDSS will be presented by visit, and for subjects who participated in Study 205MS301, by previous treatment group.

MSFC

Changes in the MSFC z-score will be summarized by study visit, and for subjects who participated in Study 205MS301, by previous treatment group. For subjects in Study 205MS301 and Study 205MS303 ITT population, MSFC z-score may be summarized over the combined study period (Studies 205MS301 and 205MS303). Details on the calculations of the z-score for each component will be described in the statistical analysis plan.

SDMT

Changes in the SDMT scores will be summarized by study visit and by previous treatment group in Study 205MS301. Change in the SDMT scores over the combined study period (Studies 205MS301 and 205MS303) will be calculated using the Study 205MS301 baseline visit

CONFIDENTIAL

The information contained herein may not be used, disclosed, or published without the written consent of Biogen MA Inc.

as baseline. Change in the SDMT score over the Study 205MS303 study period will be calculated using the last SDMT measurement in Study 205MS301 as baseline.

PASAT 3

Changes in the PASAT 3 scores will be summarized by study visit and by previous treatment group in Study 205MS301. Change in the PASAT 3 scores over the combined study period (Studies 205MS301 and 205MS303) will be calculated using the Study 205MS301 baseline visit as baseline. Change in the PASAT 3 score over the Study 205MS303 study period will be calculated using the Week 0/baseline visit as baseline.

MRI Endpoints

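### Section 16.4.2 claims an overall 5% Type I error for all tests yet rules out multiplicity adjustment; 5% can only be a per-test level (minor wording correction)

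*Protocol*

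**What the plan says.** All of the protocol's testing language is in Section 16.4.2, which states: "All statistical tests will be 2-sided with an overall Type I error of 5%. Adjustments for multiple comparisons will not be considered".

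The same section sets the general character of the work: "Analyses will generally be descriptive in nature and will focus on data collected during Study 205MS303 only". It then names one kind of comparison, as an option: "statistical comparisons may be made between efficacy in Study 205MS301 and efficacy in Study 205MS303 among subjects previously randomized to Avonex in Study 205MS301". No endpoint list or number of tests is attached to it.

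Section 16.4.5 gives models for three outcomes:
- For relapses: "A negative binomial regression model will be used to estimate the adjusted ARR".
- For new or newly enlarging T2 lesions, also negative binomial regression.
- For change in lesion volume, analysis of covariance.

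The primary endpoint in Section 6.2.1 is "Incidence of AEs and SAEs", which Section 16.4.3 summarises without naming a test. Section 16.6 says there is no formal sample size calculation. Section 16.5 plans no formal interim analysis but lets the sponsor run analyses before the end of the study.

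**The concern.** Attached to all statistical tests, the phrase overall Type I error ordinarily means the chance of at least one false positive across the whole set. Holding that at 5% needs some device: a fixed test order, a split of alpha, a single designated test or an adjustment. The next sentence excludes adjustment, and nothing elsewhere in the protocol supplies another device. The two sentences therefore agree only if exactly one test is run.

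What is at stake is how a p-value would be read. Section 6.1.2 has a secondary objective on the efficacy of switching to DAC HYP after long-term interferon beta-1a. The optional comparison between the two studies serves that objective and could be applied to more than one efficacy outcome. A significant result there would be reported under an error rate that the plan does not deliver.

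**Working it through.** **Inputs.**
- Stated overall error: 5%, two-sided, all tests (Section 16.4.2).
- Adjustment: none (Section 16.4.2), so each test is run at 0.05.
- Number of tests, k: not given, so an assumption. I use k = 2 as the smallest case beyond one test, and k = 3 for the three modelled outcomes of Section 16.4.5.
- Correlation between test statistics: not given, so an assumption. I use 0 (independence), 0.5 and 0.8.

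**Step 1: the plan's own figure.** For independent tests, each at level 0.05, the overall error is 1 − (1 − 0.05)^k. With k = 1 this is 1 − 0.95 = 5.0%. The stated figure is reproduced at k = 1 and at no larger k.

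**Step 2: independent tests.**
- k = 2: 1 − 0.95² = 1 − 0.9025 = 9.75%.
- k = 3: 1 − 0.95³ = 1 − 0.8574 = 14.3%.

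**Step 3: correlated tests.** Outcomes measured in the same subjects are plausibly positively correlated, which lowers the overall error. Take equicorrelated normal statistics Zᵢ = √ρ·S + √(1 − ρ)·eᵢ, with S and the eᵢ independent standard normal, and count how often any |Zᵢ| exceeds the two-sided 5% critical value. In 400,000 simulated draws:

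| Tests | ρ = 0 (formula) | ρ = 0.5 | ρ = 0.8 |
|---|---|---|---|
| 2 | 9.75% | 9.1% | 7.8% |
| 3 | 14.3% | 12.5% | 9.9% |

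Correlation narrows the gap but does not close it. Only perfectly correlated tests, in effect one test, would return 5%.

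**Step 4: what keeping the overall claim would need.** Bonferroni with three tests sets each at 0.05/3 = 0.0167. For independent tests the overall error is then 1 − (1 − 0.0167)³ = 4.9%. This is the kind of adjustment that Section 16.4.2 excludes.

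**The case against.** The strongest reply is that little depends on this sentence. The study is single-arm and generally descriptive, the one named comparison is optional, and the primary safety endpoint is only summarised. No sample size or stopping rule uses the 5%. The sentence that follows also tells the reader that nothing will be adjusted, so many would take 5% as the per-test level anyway. All of that stands, and it keeps the point minor. It does not make the statement correct: if a per-test level is meant, the word overall is wrong.

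A second reply is that multiplicity belongs in the statistical analysis plan. That would answer a complaint that detail is missing. Here the protocol makes a positive statement that does not hold. An analysis plan that added adjustment would contradict the protocol's second sentence, and one that did not would inherit the incorrect claim.

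A reader might also infer much larger figures by counting endpoints. Section 6.2.2 has 17 secondary bullets, the first of which ("Relapse outcomes: annualized relapse rate (ARR) and proportion of subjects who relapse") already holds two measures. Seventeen independent tests would give 58%, and the 13 bullets from relapse outcomes through the productivity questionnaire would give 49%. The document does not support these as properties of the plan:
- Four of the 17 bullets are laboratory changes, local tolerability, anti-drug antibodies and neutralizing antibodies. They are not efficacy outcomes and fall outside the one named comparison.
- Most of the other 13 are only summarised or estimated. Quality-of-life, MSFC, SDMT and PASAT 3 scores are summarised by visit. Relapse and progression proportions come from Kaplan-Meier curves with no test named.
- Results by previous treatment group may be summarised; Section 16.4.2 does not say they will be tested against each other. Outputs by visit and by time interval are likewise mainly summaries.

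Even for the three modelled outcomes, the relapse model is described as estimating a rate. The k = 3 figures are therefore illustrations of scale.

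**Conclusion.** The two sentences in Section 16.4.2 cannot both hold once more than one test is run, and the protocol does not confine itself to one. The overall error would be 9.75% for two independent tests. For the three modelled outcomes it would be between 9.9% (correlation 0.8) and 14.3% (independence). These figures assume the stated number of tests, each at an unadjusted two-sided 5%, with all null hypotheses true. The protocol fixes neither the number nor the correlation.

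The effect is confined to the optional comparisons of efficacy between the two studies in former Avonex subjects and to any tests drawn from the three models. A reader might go on to infer that the safety conclusion is weakened or that a multiplicity procedure is required. Neither follows: the primary analysis uses no test, and unadjusted exploratory testing is acceptable in a descriptive extension study. The error lies in the claim of overall control. Minor severity.

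**What to change.** Replace the two sentences in Section 16.4.2 with:

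> Any statistical test will be 2-sided at a nominal 5% level per test; no adjustment for multiple comparisons will be made, the overall Type I error is not controlled, and p-values are exploratory.

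This keeps the sponsor's choice not to adjust and changes no data collection, sample size or model. The cost is one sentence and a less favourable statement of error control. If the sponsor wants to make confirmatory claims on the switch from Avonex, it would instead have to name the tests in advance and control the error across them, which is a larger change than this study needs.
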